[figure not shown]

**Secondary Objectives:**

- To evaluate the efficacy of GS010 compared with sham over the follow-up period and at Week 96 in the change from baseline of the LogMAR.
- To verify whether the efficacy at Week 48 and at Week 96 of GS010 compared with sham and measured by the change from baseline in the LogMAR is dependent upon the treatment of the better- or worse-seeing-eye.
- To verify whether the rate of responders at Week 48 and 96 is dependent upon the treatment received and whether the magnitude of the treatment effect is dependent upon the treatment of the better- or worse-seeing eye at entry.
- To assess the effect of GS010 on parameters measured with high resolution SD-OCT
- To assess the effect of GS010 on standardized automated visual fields obtained with the Humphrey Visual Field (HVF) Analyzer II.
- To assess the effect of GS010 on contrast sensitivity measured with the Pelli-Robson chart.
- To assess the effect of GS010 on color vision measured with the Farnsworth-Munsell 100 Hue color test.

[REDACTED]

[REDACTED]

[REDACTED]

[REDACTED]

[REDACTED]

[REDACTED]

**3. STUDY DESIGN**

**3.1 OVERALL DESIGN**

GS-LHON-CLIN-03A is a Phase III double-masked, sham-controlled, multicenter, multi-country study. Recruitment is competitive.

Both eyes will receive standard antiseptic preparation, administration of topical local ocular anesthetic agents and will undergo pupillary dilation. Administration of an intra-ocular pressure lowering agent will precede treatment. GS010 will be administered once during the study via a

## 3.2 DURATION AND SCHEDULE OF STUDY PARTICIPATION

### Study Schedule

The trial is divided into the following visits:

**Screening Visit (Visit 1):** From 28 to 2 days before the investigational medicinal product (IMP) administration. This visit will allow Investigators to assess subject eligibility based on selection and non-selection criteria.

**Inclusion Visit (Visit 2):** 1 day before the IMP administration. This visit will allow Investigators to confirm the subject's eligibility based on inclusion and exclusion criteria. Subjects will undergo baseline ophthalmic testing.

After the subject is confirmed to be eligible for the study, the right eye will be randomized to GS010 or sham treatment based on a predefined central randomization scheme.

**Treatment Visit (Visit 3):** Day of the IMP administration. Subjects will receive GS010 by IVT injection according to the randomized treatment assigned. The fellow eye will receive the alternative treatment.

**Follow-up visits (Visits 4 to 12):** Nine follow-up visits after the IVT procedure will be conducted at 24 hours and 2, 4, 8, 12, 24, 48, 72, and 96 weeks.

The study plan is shown in Section 4.2 of V3.0 of the protocol.

### Study duration:

Initiation of the trial with the first subject's first visit is planned for late Q4 2015. The estimated recruitment period is 12 months and will be dependent on recruitment rate. Total study follow-up is 96 weeks and the study will end with the last subject's last visit. The last subject's last visit is estimated to occur late Q4 2018. Therefore, the estimated study duration is 3 years.

At the end of this initial study period, a long-term safety and efficacy study as detailed in a future separate protocol will be initiated for further evaluation of the safety and efficacy durability. The long term safety study duration will be conducted according to current regulatory authority recommendation.

## 3.3 SAMPLE SIZE CONSIDERATIONS

Sample size calculation is based on the primary endpoint (LogMAR) and on the paired comparison of treated and sham eye. There is no published data regarding the within subject variance and the sample size calculation through paired comparison will therefore be very speculative for two reasons. The first reason is the within subject correlation between right and left eye and the second reason is the absence of information on the within and between subject variance of the LogMAR. Usually the within subject correlation is positive and the use of a null correlation is conservative. The absence of information on the LogMAR requires a second rough

approximation of the mean and variance of LogMAR because the mean of ETDRS (Lam et al. 2014) is highly correlated to the variance of ETDRS ( $R^2 = 0.839$  for the log-log relationship). This correlation is in favor of the use of the LogMAR to stabilize the variance but the transformation from ETDRS mean and variance to LogMAR mean and variance requires additional assumptions. Starting with a mean 23.4 and a standard deviation of 28.3 (Lam et al. 2014) and a difference of 20 letters on average between treated and sham eye, using the relationship between the log mean and the log variance obtained with Lam et al. (2014) results (log variance =  $1.743 \log \text{mean} + 0.48$ ,  $R^2 = 0.839$ ) and assuming a perfect lognormal distribution of ETDRS, the difference in means of the lognormal distributions is 0.65 (3.32 - 2.67) and the pooled standard deviation of the log distributions is 0.914. Assuming no correlation between both eyes, the within subject standard deviation is  $(2 \times 0.914^2)^{0.5} = 1.29$ . The standardized difference in means is therefore  $0.65/1.29 = 0.504$  rounded to 0.50. The sample size required to get a power of 85% is exactly 36 subjects.

In GS-LHON-CLIN-01(Phase I/II study), at Week 48 the standard deviation (SD) for visual acuity of the between-eye difference in change from baseline was calculated as 0.594. Considering that in Phase III studies of GS010 detection of a 15 ETDRS letters or 0.3 LogMAR difference between treated and untreated eyes at outcome is a clinically reliable difference, the SD of the difference of 0.594 would provide a power/probability of 84% to detect such a difference based on the enrolment goal of 36 subjects each in the RESCUE and REVERSE Phase III clinical trials.

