12.2 Sample Size

Sample size calculation is based on the primary endpoint (LogMAR) and on the paired comparison of treated and sham eye. There is no published data regarding the within subject variance and the sample size calculation through paired comparison will therefore be very speculative for two reasons. The first reason is the within subject correlation between right and left eye and the second reason is the absence of information on the within and between subject variance of the LogMAR. Usually the within subject correlation is positive and the use of a null correlation is conservative. The absence of information on the LogMAR requires a second rough approximation of the mean and variance of LogMAR because the mean of ETDRS (Lam et al. 2014) is highly correlated to the variance of ETDRS ($R^2 = 0.839$ for the log-log relationship). This correlation is in favor of the use of the LogMAR to stabilize the variance but the transformation from ETDRS mean and variance to LogMAR mean and variance requires additional assumptions. Starting with a mean 23.4 and a standard deviation of 28.3 (Lam et al. 2014) and a difference of 20 letters on average between treated and sham eye, using the relationship between the log mean and the log variance obtained with Lam et al. (2014) results (log variance = 1.743 log mean + 0.48, $R^2 = 0.839$) and assuming a perfect lognormal distribution of ETDRS, the difference in means of the lognormal distributions is 0.65 (3.32 - 2.67) and the pooled standard deviation of the log distributions is 0.914. Assuming no correlation between both eyes, the within subject standard deviation is $(2x0.914^2)^{0.5} = 1.29$. The standardized difference in means is therefore 0.65/1.29 = 0.504 rounded to 0.50. The sample size required to get a power of 85% is exactly 36 subjects.

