#### Primary Analysis for EMA

The null and alternative hypotheses for the primary endpoint are defined below

$$H_0: \mu_{\text{All-GS010}} = \mu_{\text{All-Sham}}$$

$$H_1: \mu_{\text{All-GS010}} \neq \mu_{\text{All-Sham}}$$

Where  $\mu$  presents the mean change from baseline to Week 48 in LogMAR. “All” represents all eyes treated with GS010 or Sham

The primary analysis will be performed on the ITT population. The change from baseline to Week 48 in the LogMAR acuity will be the primary response. The change from baseline of all-GS010 eyes will be compared to the change from baseline of all-Sham eyes (intra-subject comparison) using a mixed model of analysis of covariance (ANCOVA) using the following terms (or covariate) in the model:

- Subject as random factor
- Eyes of the subject as random factor,
- Treatment and the
- Baseline LogMAR for each eye.

The analysis will be performed based on alpha of 0.05. The statistical significance in favor of GS010 against sham will provide evidence of the advantage of using GS010 for halting visual acuity loss or improving visual acuity in subjects with LHON with duration of vision loss of 6 months or less. The difference in the mean change from baseline (adjusted mean difference) to Week 48 between the two treatment groups and associated 95% confidence interval will be reported.

The center will not be included in the analysis as the number of subjects recruited per site will be very small. However, stratification by geographical area will be performed as a sensitivity analysis. Neighboring countries can be pooled together to reach at least 9 subjects per geographical entity. The pooling will be performed during the masked review of data.

All the model diagnostics will be checked.

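### SAP 3.3 quotes 85% and 84% power for the same 36 pairs by what appear to be two different methods; the 85% holds only under the normal approximation, and a paired t-test gives 83%

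*SAP*

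**What the plan says.** SAP 3.3 and Protocol 12.2 share one sample-size derivation. It is framed as a within-subject comparison: "Sample size calculation is based on the primary endpoint (LogMAR) and on the paired comparison of treated and sham eye". From published letter scores and a lognormal assumption it arrives at "The standardized difference in means is therefore 0.65/1.29 = 0.504 rounded to 0.50", and it concludes "The sample size required to get a power of 85% is exactly 36 subjects".

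SAP 3.3 then adds a second calculation that the protocol does not contain. It draws on the Phase I/II study: "at Week 48 the standard deviation (SD) for visual acuity of the between-eye difference in change from baseline was calculated as 0.594". It takes as its target that "detection of a 15 ETDRS letters or 0.3 LogMAR difference between treated and untreated eyes at outcome is a clinically reliable difference", and states that this SD "would provide a power/probability of 84% to detect such a difference based on the enrolment goal of 36 subjects each" in the two Phase III trials.

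Neither paragraph names a test, a formula, an alpha or a sidedness. Alpha appears later, under the primary analysis for EMA in SAP 9.5.1: "The analysis will be performed based on alpha of 0.05". The alternative hypothesis there is two-sided.

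**The concern.** Both paragraphs describe the same kind of comparison, treated eye against sham eye, with the same 36 subjects. The second standardized difference (0.505) is slightly larger than the first (0.504, rounded to 0.50), yet the second power is lower (84% against 85%). For one test at a fixed sample size and alpha, power can only rise with the standardized difference. The two figures therefore cannot come from one method, and the text does not say which method either used.

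What is at stake is modest. The 85% is the protocol's only stated power for the choice of 36 subjects, and it is presented as an exact requirement. A reader who puts the two paragraphs side by side finds two figures in the wrong order and no stated basis for either.

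**Working it through.** **Inputs**

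- Number of pairs: n = 36 (Protocol 12.2, SAP 3.3).
- First standardized difference: 0.65/1.29 = 0.504, rounded in the plan to 0.50.
- Second standardized difference: 0.3/0.594 = 0.505. The SAP does not print this ratio.
- Alpha 0.05, two-sided: taken from SAP 9.5.1. Applying it to the sample-size section is an assumption.

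**Step 1: reproduce the plan's 36 and 85%.** The paired normal approximation is n = ((z₀.₉₇₅ + z₀.₈₅)/d)². With d = 0.50 this is ((1.960 + 1.036)/0.50)² = 35.91, rounded up to 36. Power at 36 is Φ(d√36 − 1.960) = Φ(3.00 − 1.960) = Φ(1.040) = 85.1%. The plan's first figure reproduces.

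**Step 2: apply both methods to both paragraphs.** The paired t-test power comes from the noncentral t distribution with 35 degrees of freedom, critical value 2.030 and noncentrality d√36.

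| Standardized difference | Normal approximation | Paired t-test | Stated in the plan |
|---|---|---|---|
| 0.50 (first paragraph, rounded) | 85.1% | 83.1% | 85% |
| 0.504 (first paragraph, unrounded) | 85.6% | 83.6% | not stated |
| 0.505 (second paragraph) | 85.8% | 83.8% | 84% |

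The first stated figure matches the normal column and the second matches the t-test column. On one method the pair would read about 85% and 86% (normal), or 83% and 84% (t-test).

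**Step 3: can rounding or sidedness explain it?** If the SD of 0.594 was rounded from anywhere between 0.5935 and 0.5945, the second paragraph gives 83.7% to 83.9% by t-test and 85.7% to 85.8% by normal approximation. The printed 84% is therefore still the t-test value. A one-sided alpha of 0.05 gives 90% to 92% by either method and matches neither figure.

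**Step 4: what 85% needs under the t-test.** At d = 0.50 the power is 83.1% with 36 subjects, 84.1% with 37 and 85.1% with 38. At the unrounded 0.504, 37 subjects give 84.7%, so 38 are still needed.

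**Step 5: sensitivity to the between-eye correlation.** The first calculation sets this correlation to zero. With correlation r and the other inputs unchanged, the SD of the difference shrinks by √(1 − r), so d = 0.50/√(1 − r). The documents give no value for r; the values below are assumptions.

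| r | d | Paired t-test power, n = 36 |
|---|---|---|
| 0 | 0.500 | 83.1% |
| 0.05 | 0.513 | 84.9% |
| 0.06 | 0.516 | 85.3% |
| 0.10 | 0.527 | 86.7% |

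**The case against.** The strongest reply is that there is no arithmetic error. A standard planning formula returns 35.91, hence 36 subjects and 85.1% power, and each stated figure is right by its own method. This stands. A reader might infer that the 85% is simply wrong, or that the true type II error is 17% and not 15%. The documents do not support either reading. They fix no test, alpha or sidedness for the sample size, and a plain paired t-test is not the primary analysis. For EMA that analysis is a baseline-adjusted mixed model, and for FDA a between-subject ANCOVA in best-seeing eyes (SAP 9.5.1). A one-sample t-test on the between-eye difference appears only as a missing-data sensitivity analysis in Protocol 12.7. The 83% is thus a benchmark for the comparison on which the trial was sized, not the power of the planned models.

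The second reply is that the gap is smaller than the uncertainty the plan already admits. The plan describes its calculation as highly speculative and its zero correlation as conservative. This stands too, and it rules out the inference that the trial is too small.

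The third reply is that the two paragraphs are visibly different calculations, one from published letter scores and one from the Phase I/II SD. That is true of their inputs, but once reduced to standardized differences they describe the same paired problem. Different sources for the inputs cannot put the two powers in the wrong order.

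**Conclusion.** The inconsistency is real and minor. SAP 3.3 gives two powers for 36 pairs that no single method can produce. The best explanation is a normal approximation in the first paragraph and a paired t-test in the second, although the documents do not say so.

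Calling 36 the exact requirement for 85% holds only if the variance is treated as known. It will in fact be estimated from the data. With a two-sided alpha of 0.05 and a standardized difference of 0.50, the paired t-test gives 83.1%, about 2 points lower, and reaches 85% at 38 subjects, 2 more than planned. This conclusion takes the plan's 0.50 as given and rests on carrying the alpha and sidedness of SAP 9.5.1 back to the sample-size section. It is a matter of stated method and wording, not evidence that the sample size should change.

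**What to change.** Keep 36 subjects. In SAP 3.3 and Protocol 12.2, delete *exactly* and replace the concluding sentence of the first calculation with wording such as:

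> With 36 subjects, a two-sided 5% paired t-test has about 83% power at a standardized difference of 0.50 (84% at 0.504).

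In the second paragraph of SAP 3.3, keep the 84% for 0.3 LogMAR with an SD of 0.594 and say that it is on the same basis. Add one sentence stating that the paired t-test is a planning benchmark, and that the primary analyses are the baseline-adjusted mixed model (EMA) and the between-subject ANCOVA in best-seeing eyes (FDA).

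The cost is a few lines in SAP 3.3, mirrored in Protocol 12.2 at its next amendment. No patients are added and no analysis changes. The only downside is a stated power about 2 points lower.

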### 3.4 RANDOMIZATION

The right eye of each subject will be randomly allocated to receive either GS010 or sham treatment in a 1:1 allocation ratio. The fellow (left) eye will receive the treatment not allocated to the right eye. Therefore, each subject will receive GS010 in one eye and sham treatment in the fellow eye. Prior to randomization, each subject's best- and worst-seeing eye will be determined. Efron's minimization method will be used in the randomization process to balance as much as possible the two treatment groups (GS010 and sham) in the best-seeing eyes.

To enroll a subject (Visit 1), the Investigator will call an interactive response system (IRS) and provide brief details about the subject to be enrolled. Each subject will receive a subject number assigned at screening, which will serve as the subject identifier throughout the study. The subject number will be required in all communication between the Investigator (or designee) and the IRS regarding a particular subject. Subject numbers will be tracked via the IRS.

To randomize a subject (Visit 2), the Pharmacist (or designee) will call the IRS and provide brief details about the subject to be randomized. Eligible subjects will be randomized in a 1:1 ratio (right/left eye), taking into account the Efron's minimization method, using the IRS.

The IRS User Guide will describe the steps of the randomization process from the subject's screening up to before IVT injection.

An algorithm with a testing hierarchy will be employed prior to randomization to determine the best- and worst-seeing eye of each subject, as follows:

1. ETDRS visual acuity score for subjects able to read the ETDRS chart. The eye with the higher ETDRS score is the best-seeing eye. For subjects who cannot read the ETDRS chart (“off chart” subjects) a standard study procedure will be used to determine visual acuity based on counting fingers at a given distance. The eye with the best visual acuity based on this method is the best-seeing eye. If one eye of a subject is able to read letters on the ETDRS chart and one eye cannot, the eye able to read the ETDRS chart is the best-seeing eye.
2. SD-OCT parameters (to be used if there is no inter-eye difference based on Criterion 1):
  - i) The initial SD-OCT parameter will be the total volume of the RGC layer of the macula. The best-seeing eye will have the greater volume and quadrant thickness, unless there is macula edema. A difference of  $\geq 5\%$  is considered significant to determine greater volume.
  - ii) The second SD-OCT parameter (to be used if there is no inter-eye difference in criteria 2i) will be the combined volume of the RGC layer of the inner and outer nasal quadrants of the macula. The best-seeing eye will be the eye with greater volume. A difference of  $\geq 5\%$  is considered significant to determine greater volume.
3. Contrast sensitivity measured with the Pelli-Robson chart (to be used if there is no inter-eye difference in criteria 1 or 2). The eye with the best Log CS (contrast sensitivity) score is the best-seeing eye.
4. If the best-seeing eye is not possible to be determined based on any of the criteria in the algorithm above, the masked investigator will determine the best-seeing eye based on the totality of the Visit 1 vision testing results and subject testimony.

Perceptive Solution, an IRS company, will be responsible for the randomization code generation and actual randomization.

## **4. STUDY VARIABLES AND COVARIATES**

### **4.1 PRIMARY VARIABLE**

The primary endpoint will be the ETDRS visual acuity (quantitative score) at Week 48 after IVT injection. The subjects’ LogMAR scores, which are derived from the number of letters read on the ETDRS chart, will be used for statistical analysis purposes. LogMAR scores for subjects unable to read the ETDRS chart (i.e. off-chart subjects) will be obtained per the pre-defined Standard Operating Procedure and the protocol. The change from baseline in each eye will be the primary response of interest.

### 4.3 PREDETERMINED COVARIATES AND PROGNOSTIC FACTORS

RGC layer, INL, ONL thickness/volume and topographical maps of these anatomical regions, best or worst-seeing eye (eye status) as determined prior to randomization and duration of vision loss at the time of treatment could be significant prognostic factors for the treatment effect. Sensitivity analysis will be performed for RGC layer thickness/volume and topographical map and eye status (best or worst-seeing eye) and duration of vision loss at the time of treatment by including them in the primary model as a covariate.

## 5. DEFINITIONS

### 5.1 STUDY DAY

All study days on or after the treatment administration will be calculated as date of assessment minus date of treatment administration +1. Study days before the treatment administration will be calculated as date of assessment minus date of treatment administration. In case of missing or incomplete dates no study days will be calculated.

### 5.2 BASELINE

The baseline value is defined as the last non-missing value prior to the start time of treatment administration (Visit 3). If assessment and treatment administration occur on same day and time is not captured, it will be considered as baseline. For OCT parameters baseline is defined as average of Visit 1 and Visit 2 assessments.

### 5.3 NADIR

The Nadir value for a given post-baseline visit is defined as the lowest value prior to and including the post-baseline visit of interest. Week. Time to Nadir in days is calculated as (Visit date at Study Nadir Value-Start date of treatment+1)

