Responder will be defined for the eyes which were On-Chart eyes at baseline and which have an improvement of at least -0.3 LogMAR or which were Off Chart at baseline but became On Chart with at least 5 ETDRS letters at a particular visit

Criteria 14

Responder eye will be defined not legally blind both at baseline and Week 48/72/96 (LogMAR < 1.0 or Snellen > 20/200)

Criteria 15

Responder will be defined by an improvement of at least -0.2 LogMAR compared to post-treatment Nadir. Early discontinuations will be considered as non-responder for both eyes.

Criteria 16

Responders will be defined by an improvement of at least -0.3 LogMAR compared to post-treatment Nadir. Early discontinuations will be considered as non-responder for both eyes.

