## ETDRS/LogMAR and on-chart and off-chart:

- I. 1 ETDRS line = 5 letters
- II. 1 ETDRS line = 0.1 LogMAR
- III. 0.1 LogMAR = 5 ETDRS letters
- IV. 15 ETDRS letters = 0.3 LogMAR
- V. A less positive/more negative LogMAR is an improvement of vision
- VI. An increase in the number of ETDRS letters read is an improvement of vision

On-Chart subjects: defined as being able to read at least 3 ETDRS letters on a single line on the ETDRS chart at either 4 or 1 meters

- a. Have an obtainable Snellen equivalent obtained directly from ETDRS chart
- b. Each Snellen equivalent is assigned a LogMAR value

Off-chart Subjects: defined as a subject who cannot read at least 3 ETDRS letters on a single line of the ETDRS chart at either 4 or 1 meters and thus have no Snellen equivalent obtainable from ETDRS chart

- c. These subjects are categorized as able to either count fingers (CF), detect hand motion (HM), detect light perception (LP) or are no-light perception (NLP)
- d. For those categorized as either CF or HM a method for deriving LogMAR visual acuity is pre-specified
- e. The distance at which CF/HM vision was obtained is recorded per the standard operating procedure
- f. Study database derives the LogMAR based on this distance and the finger/hand dimensions of the examiner, per pre-specified method.

Treatment-Emergent Adverse Events (TEAE)

Treatment-emergent adverse events (TEAEs) are defined as AEs that started after study treatment administration at Visit 3 or that represent an exacerbation of a condition that is present at baseline after treatment administration. Worsening of visual acuity determined by the investigator to be due to progression of LHON will not be considered as an AE. Any AE with an unknown start date will be considered treatment-emergent if the event does not stop prior to study treatment administration. AEs with partial dates are described in [Section 5.7.2](#).

Prior and Concomitant Treatment

Prior treatments will be defined as any treatments with start date and time prior to the study treatment administration date and time.

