#### Other Analysis

Summary statistics for LogMAR and ETDRS score and change from baseline will be presented by treatment group (All-GS010/All-Sham).

Summary statistics for LogMAR and change from baseline will be presented by treatment group for on chart eyes at baseline (All-GS010/All-Sham).

Summary statistics for LogMAR and change from Nadir and time to Nadir will be presented by treatment group (All-GS010/All-Sham).

A graph presenting the mean of each treatment group at baseline and the mean at all the timepoints (Week 48,72 and 96)Week will be presented. The graph will be useful to assess whether the difference in the change from baseline is mainly due to the difference at baseline or the difference at Week 48.

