### **9.5.3 Multiplicity**

All the type I error ( $\alpha=0.05$ ) will be spent for the primary end point analysis. All the other analysis will be supportive analysis of the primary end point. Therefore, no adjustment of multiplicity will be necessary.

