### Eye responders

The responder analyses at both Week 48 , Week 72 and Week 96 will be based on a McNemar test comparing all-GS010 eyes against all-Sham eyes.

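### SAP 5.3 defines nadir as the lowest value. On LogMAR that is the best acuity so far, so Eye Responder Criteria 15 and 16 cannot be met as written

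*SAP*

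**What the plan says.** SAP 5.3 gives one definition and names no scale: "The Nadir value for a given post-baseline visit is defined as the lowest value prior to and including the post-baseline visit of interest". It then computes time to nadir as the date of the visit with the study nadir value, minus the treatment date, plus one day.

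In the text available, nadir is used in two places, both on LogMAR:

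- SAP 5.6, Additional Responder Definitions, Eye Responder. Criteria 15: "Responder will be defined by an improvement of at least -0.2 LogMAR compared to post-treatment Nadir". Criteria 16: "Responders will be defined by an improvement of at least -0.3 LogMAR compared to post-treatment Nadir".
- SAP 9.5.1, Other Analysis under the EMA primary analysis: "Summary statistics for LogMAR and change from Nadir and time to Nadir will be presented by treatment group".

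SAP 5.6 fixes the direction of each scale. For LogMAR: "A less positive/more negative LogMAR is an improvement of vision". For letters: "An increase in the number of ETDRS letters read is an improvement of vision".

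SAP 9.5.5 analyses eye responders at Weeks 48, 72 and 96, "based on a McNemar test comparing all-GS010 eyes against all-Sham eyes". SAP 9.5.3 gives the standing of everything beyond the primary analysis: "All the other analysis will be supportive analysis of the primary end point".

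**The concern.** Nadir normally means the worst point of a course. The definition picks the smallest number, and on LogMAR the smallest number is the best vision. Criteria 15 and 16 ask how far an eye has recovered from its nadir. If the nadir is the eye's best value to date, there is nothing to recover from.

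The outputs at stake are meant to show recovery after a decline. That course is plausible here: Protocol 5.2.1 admits subjects with vision loss in only one eye, and the study summary gives a median delay of 2 months before the second eye is involved. A literal derivation would remove this information from the responder tables. In the descriptive summaries it would report the best visit under the label of the worst.

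**Working it through.** The plan gives no figure to reproduce. The check is algebra on the definitions, followed by an example.

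**Inputs**
- Nadir at visit v, N(v): the minimum of the values up to and including v (SAP 5.3).
- LogMAR: lower is better (SAP 5.6). SAP 5.7.1 agrees, assigning 4 to light perception and 4.5 to no light perception.
- Criteria 15 and 16: X(v) - N(v) ≤ -0.2 and ≤ -0.3, where X(v) is the LogMAR at visit v (SAP 5.6).
- Planned enrolment: 36 subjects, one GS010 eye and one sham eye each (Protocol 5.1 and 8.6).

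**Step 1: the inequality.** The set over which the minimum is taken contains X(v) itself, so N(v) ≤ X(v) and X(v) - N(v) ≥ 0. Adding baseline can only lower the minimum, so the result is the same with or without it. Taking the minimum over the whole study also leaves the difference at or above 0. Neither -0.2 nor -0.3 can occur.

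**Step 2: the responder tables.** Responders are 0/36 per arm for each criterion at each visit. If SAP 9.5.5 covers these criteria, there are 2 criteria × 3 visits = 6 McNemar comparisons. Each has discordant counts b = c = 0, so (b - c)²/(b + c) = 0/0.

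**Step 3: an example eye (assumed values).**

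| Week | 2 | 4 | 8 | 12 | 24 | 48 |
|---|---|---|---|---|---|---|
| Day | 14 | 28 | 56 | 84 | 168 | 336 |
| LogMAR | 1.1 | 1.3 | 1.5 | 1.6 | 1.4 | 1.2 |

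| At Week 48 | Lowest value (as written) | Highest value (worst vision) |
|---|---|---|
| Nadir | 1.1 | 1.6 |
| Change from nadir | 1.2 - 1.1 = +0.1 | 1.2 - 1.6 = -0.4 |
| Time to nadir | 14 + 1 = 15 days | 84 + 1 = 85 days |
| Criteria 15 and 16 | neither met | both met |

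At 5 letters per 0.1 LogMAR (SAP 5.6), -0.4 is a gain of 20 letters. The times use post-treatment visits only and assume that no later visit falls below 1.1 (left column) or rises above 1.6 (right column). If an assumed baseline of 0.9 is put in the set, the literal change becomes 1.2 - 0.9 = +0.3, and the criteria still fail.

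**Step 4: numerical confirmation.** In 200,000 arbitrary LogMAR paths over the eight visits from Week 2 to Week 96 (assumed baseline mean 1.3 and SD 0.5, step SD 0.25), the smallest change from the literal nadir was 0.0. No eye met either criterion at Weeks 48, 72 or 96, with baseline in or out. With nadir read as the worst post-treatment value, 54.2% met Criteria 15 and 43.8% met Criteria 16 at Week 48. Those shares show only that the criteria become attainable; they predict nothing about the trial.

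**Step 5: the other scale.** On ETDRS letters the same sentence would pick the worst visit, because fewer letters is worse. The wording fits letters and fails on LogMAR, which is the scale the SAP uses it on.

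**The case against.** The best defence is that the intent is clear. Improvement relative to a nadir makes sense only if nadir means lowest vision, so a competent programmer would take the highest LogMAR. That is probably what was meant. But the definition speaks of the lowest value, and a derivation that follows it takes the minimum. Elsewhere the documents use the word *worst* when they mean it (SAP 5.7.1, Protocol 12.7). Nothing in the available text defines the LogMAR nadir as the highest value. The table shells and derivation specifications are not available, so a correction there cannot be excluded.

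A second defence is that the harm is small and visible. These are two of sixteen additional eye criteria, and 0% in both arms favours neither arm and would stand out at the masked data review in SAP 8.2. This is fair for the responder tables. It is weaker for change from nadir and time to nadir, where a wrong derivation still gives believable numbers.

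Third, the count of six McNemar comparisons is a reading. SAP 9.5.5 does not name Criteria 15 and 16, but it covers eye responders at three visits and excludes no criterion.

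Fourth, the window needs care. SAP 5.3 does not say whether baseline counts, and it uses the term study nadir for the time calculation. Criteria 15 and 16 say post-treatment, which supports leaving baseline out. The study nadir can be read as the running worst value at the last visit. Both belong in the corrected wording.

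**Conclusion.** The definition is wrong as written for LogMAR. Criteria 15 and 16 are unattainable for any eye under any data, and the nadir summaries point to the best visit. The inequality needs no distributional assumption. The 0/36 counts assume the planned enrolment, and the six undefined tests assume that SAP 9.5.5 applies to every eye criterion.

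The effect stops at supportive outputs. This should be fixed, but it does not threaten the trial's main conclusion.

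**What to change.** Replace the definition in SAP 5.3 with wording such as: *For LogMAR, nadir is the highest (worst) post-treatment value from Visit 5 (Week 2) up to and including the visit concerned. The study nadir used for time to nadir is this value at the subject's last visit.* Use it for change from nadir, time to nadir and Criteria 15 and 16.

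Starting at Visit 5 follows from Protocol 6.1.4.1, 7.3.1 and 12.4.5, which already keep Visit 4 acuity out of the efficacy analysis.

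The cost is this short rewording and the matching derivation code, with no new data. Make the change before the Week 48 unmasking, because Protocol Appendix V bars SAP amendments once the randomization code is broken and treats later additions as post hoc.
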